PART B STUDY DESCRIPTION

TITLE OF PROTOCOL	Virtual Reality in the Operating Room: Using Immersive Relaxation as an Adjunct to Anesthesia
Principal Investigator	[name] MD

B1. PURPOSE OF PROTOCOL

The purpose of this study is to investigate whether the use of virtual reality (VR) during wrist and hand surgery can reduce intraoperative pain and anxiety here at BIDMC through use of a randomized controlled trial. Specifically we aim to:

Specific Aim 1A: Evaluate whether the use of VR during wrist and hand surgery can lead to a reduction in intraoperative propofol dose, as compared to a usual care control.

Specific Aim 1B: Determine whether the use of VR during upper extremity surgery can lead to improvements in additional secondary outcomes, including length of postoperative anesthesia care unit (PACU) stay, postoperative pain scores and opioid doses.

Specific Aim 1C: Assess whether differences in patient satisfaction occur between individuals who do and do not receive VR during their hand/wrist procedure.

We hypothesize that the use of a virtual reality program during surgery can lead to a reduction in the dose of anesthesia needed for patient relaxation and comfort in the setting of hand and wrist operations with regional anesthesia.

B2. SIGNIFICANCE AND BACKGROUND FOR THE STUDY

There are nearly 600,000 ambulatory operations on the hand and wrist each year in the United States (Jain 2013). Currently, the standard anesthesia practice for these types of cases involves the combination of regional anesthesia (nerve block) and monitored anesthesia care (MAC). The goal of the regional anesthetic is to block both sensation and motor function to the operative area, which minimizes pain and discomfort for the patient and allows for good operating conditions for the surgeon. With an insensate and immobile extremity, the patient would ideally only require additional anesthetic agents to reduce intraoperative anxiety. In daily practice, however, such patients will commonly receive doses of intravenous sedatives, such as propofol, that most anesthesiologists would consider excessive. With the important role played by oversedation in the generation of postoperative adverse events, an intervention that could be shown to reduce intraoperative sedative requirements would prove to be very valuable (Bhananker 2006).

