PACU stay, as well as postoperative analgesia administration and pain scores. In addition, study team members will review the patients' medical records to collect demographic data and surgical characteristics including intraoperative vital signs, medication administration, and postoperative outcome data. Postoperative pain scores (i.e. 'Rate your pain on a scale from 0 to 10') are documented routinely as part of standard postoperative clinical care, and will be recorded at admission to the PACU and at PACU discharge. Additional baseline characteristics including but not limited to age, race, gender, BMI and comorbidities will be abstracted from the medical record. REDCap will be utilized for survey administration, data collection and storage.

Safety Monitoring and Reporting

This patient population is undergoing surgery and it is expected that they may have a number of unrelated adverse health events during their hospital course. Therefore, we will limit the scope of AE monitoring and reporting to the following:

- All Serious Adverse Events believed to be related to the study procedures
- All non-serious Adverse Events believed to be related to the study procedures

Adverse events will be monitored until the time of PACU discharge.

B. Statistical Considerations

Sample Size Justification: Using a two sided α of 0.05, 80% power, and mean propofol doses of 0.069 (standard deviation 0.03) and 0.042 (SD 0.021), we anticipate needing to enroll a total of 32 patients to be able to detect a 50% reduction in the mean total intraoperative propofol dose. We believe this to be a reasonable effect size given preliminary data from a related study in which investigators were able to demonstrate a >50% reduction in dose for major joint surgery (Chan 2017). In order to compensate for anticipated drop out, we will plan to enroll an additional 8 patients to bring the total planned enrollment to 40 patients, with 20 in each of the two groups.

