Data Analysis: Patients will be prospectively randomized using 1:1 block randomization of equal sizes. Analyses will be conducted using SAS version 9.3 (SAS Institute, Cary, North Carolina) or later. Descriptive statistics of the data will be performed. Continuous data will be represented using mean (\pm standard deviation) or median (interquartile range) for variables not normally distributed and compared using parametric or non-parametric t-tests as appropriate. Categorical data will be presented using proportions and compared using a chi-square or Fishers Exact test.

Primary Outcome

The primary outcome of this study is total intraoperative propofol dose, evaluated as a continuous variable. This will be assessed using a t test or Wilcoxon Rank Sum test, depending on the normality of the data. Although randomization should account for potential difference between groups, we will employ univariate and multivariable linear regression modeling to adjust for differences that persist, as necessary. Odds ratios and 95% confidence intervals will be reported. Our primary analysis will be conducted using intention to treat principles.

Secondary Outcomes

A priori secondary outcomes include length of PACU stay, postoperative analgesia dose requirements, postoperative pain scores, and overall patient satisfaction. Differences in time, medication administration and pain scores will be expressed as continuous variables. Patient satisfaction will be assessed from the REDCap survey, and will provide quantifiable estimates of satisfaction in multiple areas including but not limited to pain, anxiety, nausea, and overall experience. Adherence to the randomization assignment will be evaluated, and in the event that any patient receives an intervention different than their randomization assignment, we will also perform a per protocol analysis as an additional secondary outcome. For all secondary analyses, parametric or non-parametric tests will be employed in an analogous fashion to our baseline characteristics between groups.

C. Subject Selection

Inclusion Criteria:

1. Patients undergoing hand or wrist surgery at BIDMC under MAC

Exclusion Criteria:

1. Age < 18
2. Open wounds or active infection of the face or eye area
3. History of motion sickness
4. History of claustrophobia
5. History of seizures or other symptom linked to an epileptic condition
6. Patients who plan to wear hearing aids during the procedure

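### The plan commits to odds ratios for a continuous primary outcome, but none of the analyses it names produces one

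*Combined protocol and SAP*

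**What the plan says.** All the relevant analysis text is in section B3.B, Statistical Considerations.

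- **Outcome** (Primary Outcome): "The primary outcome of this study is total intraoperative propofol dose, evaluated as a continuous variable".
- **Test** (same paragraph): "This will be assessed using a t test or Wilcoxon Rank Sum test, depending on the normality of the data".
- **Adjustment** (same paragraph): "we will employ univariate and multivariable linear regression modeling to adjust for differences that persist, as necessary".
- **Effect measure** (the next sentence): "Odds ratios and 95% confidence intervals will be reported".

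The Data Analysis paragraph adds descriptive summaries by group: mean with SD, or "median (interquartile range) for variables not normally distributed". Categorical data have their own rule there, namely proportions with a chi-square or Fisher's exact test.

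Specific Aim 1A in section B1 asks whether VR "can lead to a reduction in intraoperative propofol dose, as compared to a usual care control". The Sample Size Justification compares mean doses of 0.069 (SD 0.03) and 0.042 (SD 0.021) and arrives at 32 patients, raised to 40 for dropout.

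**The concern.** An odds ratio needs a binary or ordered outcome and a model or table that yields odds. The primary outcome here is a dose on a continuous scale, and the methods named for it work on means or ranks. The sentence on reporting therefore cannot be carried out with the analyses that precede it.

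What is at stake is the pre-specified primary estimate. The odds ratio is the only between-group measure that the plan names for the primary outcome. The mean (SD) and median (IQR) describe each arm separately and do not supply a between-group effect with a confidence interval. If the sentence is set aside as a slip, no effect measure is explicitly pre-specified. If it is followed, someone has to bring in a model that the plan does not contain.

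**Working it through.** **1. What each named method estimates**

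| Method in the plan | Between-group quantity | Odds ratio? |
|---|---|---|
| t test | difference in mean dose | no |
| Wilcoxon rank sum test | rank-based p-value; usual companion estimate is the Hodges-Lehmann shift | no |
| Linear regression, one or several covariates | treatment coefficient = crude or adjusted mean difference | no |

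No logistic, ordinal or proportional-odds model appears anywhere in the documents, and no propofol threshold is defined.

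**2. What the sample size is built on**

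Inputs from the Sample Size Justification: means 0.069 and 0.042, SDs 0.03 and 0.021, two-sided alpha 0.05, power 80%. The paragraph does not label the arms. I take 0.069 as control and 0.042 as VR, because a reduction is expected.

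- Difference: 0.042 - 0.069 = -0.027.
- Common SD: sqrt((0.03² + 0.021²)/2) = sqrt(0.0006705) = 0.0259.
- Standardised difference: 0.027/0.0259 = 1.04.
- Normal approximation: 15 per arm, 30 in total.
- Noncentral t, pooled: power 0.787 at 15 per arm and 0.814 at 16 per arm. The smallest size reaching 80% is 16 per arm, or 32 in total, which is the plan's figure. The Welch version gives 0.811 at 16 per arm.

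So the design is powered on a difference in means.

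**3. The estimate that matches the design**

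If the planning values were observed, with SE = sqrt(0.03²/n + 0.021²/n) and a pooled t interval:

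| n per arm | SE | df | Mean difference | Expected 95% CI |
|---|---|---|---|---|
| 16 | 0.00915 | 30 | -0.027 | -0.0457 to -0.0083 |
| 20 | 0.00819 | 38 | -0.027 | -0.0436 to -0.0104 |

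These are on the plan's own dose scale.

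**The case against.** The strongest reply is that this is a slip of wording with no practical effect. The paragraph fixes the outcome, the tests and the model. Linear regression software returns a coefficient with a confidence interval, so an analyst who follows the named methods gets the right quantity, and the commitment to 95% intervals still makes sense. That is probably how the sentence arose, and it limits the weight of the point. It does not remove it, because the plan still names one between-group measure for its primary outcome and that measure is wrong.

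A second reply is that the sentence was meant for categorical data. Its position counts against this: it follows the regression sentence directly, under the primary outcome, and the rule for categorical data is elsewhere and mentions no odds ratio. A third is that the Wilcoxon test is related to the proportional-odds model. That is true, but the plan names no such model, and the test itself reports no odds ratio.

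Two stronger readings are tempting, and the documents support neither.

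- *A reader might infer that the trial will dichotomise dose and lose power.* As an illustration only, assume normal doses with the planning means and SDs. Cut-points of 0.042, 0.0555 and 0.069 would then give odds ratios of 0.23, 0.17 and 0.11, and chi-square power at 16 per arm of 0.50, 0.68 and 0.76. The cut-points and the normality are my assumptions. The plan says that dose is analysed as continuous by t test or Wilcoxon test, so the power of the primary test does not fall even if an odds ratio were also printed.
- *A reader might infer that any odds ratio would hinge on an arbitrary cut-point.* That holds for logistic regression after dichotomising. A proportional-odds model gives a common odds ratio without a chosen threshold. What the two routes share is that neither is in the plan.

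**Conclusion.** The point holds as a narrow error in the stated effect measure. The reporting sentence contradicts the outcome scale and all the methods in its own paragraph, and it fits neither Aim 1A nor the basis of the sample size. An odds ratio could be obtained only from an unplanned model: ordinal, or logistic after choosing a threshold.

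Its size is limited. Nothing changes in the hypothesis test, the type I error rate, the 32 (40 with dropout) patients or the 80% power, and the error does not threaten the validity of the trial. It should be corrected before analysis, because otherwise the primary between-group estimate is not properly pre-specified.

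The conclusion about the methods rests on the text alone. The expected intervals rest on the planning means and SDs being right and on 16 or 20 analysed patients per arm.

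**What to change.** In section B3.B, Primary Outcome, replace the odds-ratio sentence with:

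> The between-group difference in mean propofol dose (VR minus control) with 95% CI will be reported, and the adjusted mean difference with 95% CI where linear regression is used; if the Wilcoxon test is used, the Hodges-Lehmann location shift with 95% CI will be reported.

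The first clause is enough to remove the contradiction for the t test and the regression. The last clause is there because the Wilcoxon test alone yields a p-value, whereas the Hodges-Lehmann estimate (the median of all between-arm pairwise differences) stays in dose units. The plan's condition that adjustment is made only as needed is kept.

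The cost is one sentence. Tests, sample size, data collection and conduct stay as they are.

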Virtual reality (VR) has expanded in recent years from the personal entertainment industry to the medical field. It has been found in preliminary study to be safe and effective as an adjunct to standard sedative and analgesic protocols in reducing pain and anxiety for patients undergoing upper gastrointestinal endoscopy, dental procedures, dressing changes for burns, and major orthopedic surgical cases (Vazquez 2017, Furman 2009, Morris 2009, Chan 2017). To date, the use of VR during hand and wrist surgery has not been studied to reduce intraoperative anesthetic requirements and improve the postoperative patient experience. A positive result from the proposed study could lead to a change in practice, with the introduction of a non-pharmacologic, patient-led intervention, potentially reducing the burden of unnecessary oversedation while providing a satisfactory perioperative experience.

B3. DESCRIPTION OF RESEARCH PROTOCOL

A. Study Design – Overview, Methods, Procedures

Study Overview

The proposed study is a randomized, controlled trial to evaluate the effectiveness of VR as an adjunct to standard anesthetic practice for hand and wrist surgery. Patients will be randomized to undergo immersion relaxation via the use of VR during their procedure or control. In both groups patients will undergo regional anesthesia preoperatively according to standard practice. Patients will then be assessed postoperatively to assess the intraoperative propofol dose between groups, as well as secondary outcomes including patient satisfaction.

Study Procedures

Patients who meet inclusion criteria with no exclusions will be approached to provide written informed consent in the perioperative period, as detailed below (Section B6). At this time we will provide patients with a study handout to ensure complete understanding of the study (see attached). We will also ask participants to complete a brief survey about how they are feeling at baseline (see attached). This should take about five minutes to complete.

After consent and prior to surgery, patients will be randomized in a 1:1 allocation to either intraoperative VR or usual care control. Given the nature of the intervention, we are unable to blind treatment allocation.

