During their operation, after appropriate positioning has been taken place, the patient will don the VR headset and view the programming of their choice. Study team members will be available intraoperatively to assist with the implementation of the device programming. The relaxation programming will run for the duration of the operative procedure. At any time, the patient or anesthesia provider can decline to continue with the VR programming. At the end of the procedure the VR headset will be removed and standard postoperative care will commence.

Control Group

Subjects in the control group will be asked to refrain from using a VR modality intraoperatively. They will otherwise prepare for surgery and undergo perioperative care according to the current standard of care.

Follow Up

Postoperative care, including management in the PACU, will be conducted to the current standards of care. Data on postoperative outcomes, medications, and pain scores will be collected as indicated below in order to assess secondary outcomes.

After surgery, members of the study team will meet with the patient and ask them to complete a survey about their experience and overall satisfaction with the study. The survey will be built and administered using REDCap. If the patient is unable to complete the survey in-person, a link directly to the REDCap survey will be emailed to them.

Consistent with the current standard of care, patients will return to their surgeon's office for a postoperative visit, which typically occurs one month after surgery. Data from this visit, including surgical outcomes and assessment, will be passively abstracted from their medical record.

Data Collection

In order to assess our primary and secondary outcomes, data will be collected on intraoperative propofol dose, length of

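### The baseline survey has no stated analysis role, so unadjusted tests of the postoperative survey domains may forgo precision that is cheap to recover

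*Combined protocol and SAP*

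**What the plan says.** Section B3.A (Study Procedures) has the study team, at the consent contact, "ask participants to complete a brief survey about how they are feeling at baseline". The items are in an attachment that is not part of the text. The next paragraph places allocation later: "After consent and prior to surgery, patients will be randomized in a 1:1 allocation to either intraoperative VR or usual care control". On the natural reading, the survey precedes randomisation.

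After surgery the team will "ask them to complete a survey about their experience and overall satisfaction with the study" (B3.A, Follow Up). Under Secondary Outcomes in B3.B, this survey is to give "quantifiable estimates of satisfaction in multiple areas including but not limited to pain, anxiety, nausea, and overall experience".

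The method for these outcomes is set in one sentence: "For all secondary analyses, parametric or non-parametric tests will be employed in an analogous fashion to our baseline characteristics between groups". The Data Analysis paragraph of B3.B says what that means. Continuous variables are "compared using parametric or non-parametric t-tests as appropriate", and for the rest, "Categorical data will be presented using proportions and compared using a chi-square or Fishers Exact test".

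Covariate adjustment appears only under Primary Outcome. It is a regression for the propofol dose, used if needed, with no covariates named. The text gives the baseline survey no analysis use.

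**The concern.** A baseline measure taken before randomisation is the natural covariate for the same measure taken afterwards. If patients score anxiety or pain on both occasions, part of the spread in the postoperative score is between-patient variation already present at baseline. A plain two-group test leaves that variation in the error term; adjusting for the baseline score removes it in proportion to the squared correlation.

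This is of interest here because B1 gives reduction of intraoperative pain and anxiety as the trial's purpose, while among the listed outcomes anxiety appears only as a survey domain. In a trial of 40 patients only large differences on such a domain are detectable. A gain that needs no further patients or data collection is therefore worth considering. What is at stake is the efficiency of secondary comparisons, not their validity.

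**Working it through.** **Inputs from B3.B.** Two-sided alpha 0.05; power 80%; mean propofol doses 0.069 (SD 0.03) and 0.042 (SD 0.021); 32 patients, raised by 8 to 40, or 20 per arm.

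**Input not in the documents.** The correlation r between a baseline survey score and its postoperative counterpart. I take 0 to 0.7 as an assumed range.

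**Step 1: the plan's own figure.** The pooled SD is sqrt((0.03² + 0.021²)/2) = 0.0259. The difference is 0.069 − 0.042 = 0.027, which is 1.043 SD. Noncentral-t power is 78.7% at 15 per arm and 81.4% at 16 per arm, so 32 in total reproduces. Allowing for 20% dropout, 32/0.8 = 40 also reproduces. This sizing is for the propofol dose; nothing in the plan is sized on the survey.

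**Step 2: unadjusted test of a survey score.** With 20 per arm, the noncentrality is d × sqrt(20/2) on 38 degrees of freedom. Power of 80% is reached at d = 0.909 SD. The 95% confidence interval half-width is 0.640 SD.

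**Step 3: ANCOVA with one baseline covariate.** With N = 40, the variance of the treatment effect relative to the unadjusted one is

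f = (1 − r²) × (1 + 1/(N − 4)) = (1 − r²) × 37/36,

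on N − 3 = 37 degrees of freedom. The second factor is the expected price of chance imbalance in the covariate. The equivalent unadjusted sample size is 40/f.

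| Assumed r | f | Detectable difference (SD) | Power at 0.909 SD | CI half-width (SD) | Equivalent unadjusted N |
|---|---|---|---|---|---|
| Unadjusted | 1 | 0.909 | 80% | 0.640 | 40 |
| 0 | 1.028 | 0.922 | 78.9% | 0.650 | 38.9 |
| 0.2 | 0.987 | 0.904 | 80.5% | 0.636 | 40.5 |
| 0.3 | 0.935 | 0.880 | 82.5% | 0.620 | 42.8 |
| 0.5 | 0.771 | 0.799 | 89.0% | 0.563 | 51.9 |
| 0.7 | 0.524 | 0.659 | 97.2% | 0.464 | 76.3 |

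**Step 4: break-even.** Setting f = 1 gives r² = 1 − 36/37 = 1/37, so r = 0.164. Below this, adjustment costs a little precision; above it, adjustment gains.

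**Step 5: if dropout uses the full allowance.** At 16 per arm the detectable difference is 1.024 SD unadjusted. Adjusted, it is 1.043, 1.022, 0.995, 0.903 and 0.745 SD at r = 0, 0.2, 0.3, 0.5 and 0.7. Break-even is sqrt(1/29) = 0.186.

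These figures treat the score as continuous and roughly normal. For ordinal items they show the direction and rough size only.

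**The case against.** The strongest reply is that the two surveys may not measure the same thing. The baseline form asks how the patient feels. The postoperative form is described as covering experience and satisfaction, and satisfaction with an operation has no value before the operation. As the items cannot be seen, nothing in the text shows that anxiety, pain or nausea was scored at baseline or that any item repeats. B6 places consent in a surgery or pre-admission testing clinic, with no stated interval to surgery, so even a repeated item might correlate weakly. All of this stands. It makes the point conditional and rules out adjusting every survey outcome for a general feeling score, since an unrelated covariate lies on the losing side of break-even.

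A reader might go further and infer that, with 20 per arm, chance imbalance in baseline feeling undermines the unadjusted comparison. It does not. Under randomisation the unadjusted test is unbiased, and its error rate already allows for such imbalance.

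A reader might also infer that precision is certainly being wasted. The documents do not support that either: they give no correlation, and at 0.2 the gain is negligible (0.904 against 0.909 SD).

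What the reply does not remove is the asymmetry. If the baseline score predicts nothing, the loss is from 80% to 78.9% power. If the correlation is 0.5, power at the same difference rises to 89%.

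**Conclusion.** The point holds in conditional form. The plan collects a pre-randomisation survey, states no analysis use for it, and compares the postoperative survey domains with tests that ignore it. Those tests are sound but may be less precise than the data allow.

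The size depends wholly on an assumed correlation. There is practically no gain at 0.2 or below, a small one at 0.3, about 12% off the detectable difference at 0.5 (0.799/0.909 = 0.88), and about 28% off at 0.7 (0.659/0.909 = 0.72). It applies only to items or domains scored on both occasions, most plausibly anxiety or pain, which the text neither confirms nor excludes. The primary analysis and the planned 40 patients are unaffected. This is an inexpensive improvement to secondary analyses, not the correction of an error.

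**What to change.** Compare the two survey forms and list the items or domains scored on both. Then add to Secondary Outcomes in B3.B wording to this effect:

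- Any postoperative survey item or domain that is also scored in the baseline survey will be analysed by ANCOVA, with arm and the baseline score of the same domain as terms. For ordinal items, a proportional-odds model or a rank-based analogue with the same terms will be used.
- Overall satisfaction, and any other item with no baseline counterpart, will be compared with the unadjusted tests already specified.

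If the comparison finds no common items, the second rule covers everything. The plan should then say that the baseline survey is descriptive only.

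The cost is analysis-plan wording and one degree of freedom per model. The downside is about one percentage point of power on an item whose baseline score proves not to be prognostic. No new data, patients or procedures are needed.
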